9.5 Laboratory Examinations

Local laboratories may be used to determine study eligibility; however, for study analysis and reporting purposes, only values determined at a central laboratory will be used with the exception of platelet count. Platelet count analyses and pregnancy tests will be performed using local laboratory results. Local laboratories may also be used if immediate results are clinically needed.

With the exception of the above, all protocol-required laboratory assessments for the Core Phase and the Extension Phases of the study, as defined in Table 5, will be performed by a central laboratory and must be conducted in accordance with the central laboratory manual and the Schedule of Events in Table 7 and Table 8.

Repeat laboratory evaluations are allowed in cases where abnormal results are noted that are believed to be related to a potential laboratory error or a transient and/or reversible condition (e.g., clumped platelets or hemolyzed sample).

If serum chemistry, hematology, and PK blood draws are drawn from a single venous puncture, a total of 19 study-related blood draws over an approximately 90 day period are expected in the Core Phase, and 24 study-related blood draws over a 24 month period are expected in the Extension Phase.

Table 5 Clinical Laboratory Tests

Category	Parameters	
Hematology		
Complete Blood Count		
Chemistry		
Electrolytes	Bicarbonate	
	Chloride	
	Potassium	
	Sodium	
Liver Function Tests	ALT	
	AST	
	Alkaline Phosphatase	
	Total Bilirubin	
Renal Function Tests	Blood Urea Nitrogen (BUN)	
	eGFR	
Other	Glucose	
Females of Child-bearing Potential Only		
	Urine or Serum Pregnancy Test	

9.5.1 Platelet Counts

Platelet count will be assessed in all subjects at all visits in the Core Phase and the Extension Phase of the study (Table 7 and Table 8). In order to be eligible for the Core Phase of the study, the subject must have an average of 2 platelet counts $<30\times10^9$ /L with no single count $>35\times10^9$ /L. The platelet count obtained at the Screening Visit/Visit 1 and 1 other platelet count taken within 28 days on either

side of the Screening Visit (may use a historical value collected per standard of care if within 28 days of Screening) will be averaged to obtain the study eligibility platelet count value, which must be $<30\times10^9$ /L. The 2 samples must be obtained ≥24 hours and ≤28 days apart and the results must be available prior to randomization.

As subjects may continue from the Core Phase to the Extension Phase, there are no minimum platelet count requirements for the Extension Phase.

9.6 Pharmacokinetic Sampling

Plasma concentrations of avatrombopag during the Core Phase will be measured using a validated bioanalytical assay. Blood samples for the measurement of avatrombopag plasma concentrations will be collected as shown in Table 6.

Regardless of the subject's current treatment regimen (once daily, three times a week, etc.) the serial PK sampling at Visit 4 and Visit 12 must occur on a day the subject is scheduled to take their dose of study drug. If study drug has been held or the dosing regimen has changed within the past week, the serial PK samples should be collected at a visit later than Visit 4 or Visit 12. This is to ensure that serial PK samples will be obtained when the subject has been on a stable dose for at least 1 week.

Blood samples for serial PK assessments will be collected during Week 2 (Visit 4) and Week 10 (Visit 12) of the Core Phase. During these visits, subjects ≥6 years of age (Cohort 1 and Cohort 2) will have a blood sample drawn pre-dose and between 2 to 4 hours, 6 to 8 hours, and 10 to 12 hours post-dose (4 samples drawn at each visit, 2 mL each). Subjects <6 years of age (Cohort 3) will have a blood sample drawn pre-dose and at 2 to 4 hours post-dose but will be randomized in a 1:1 ratio, stratified by treatment group, to either the 6 to 8 hour or the 10 to 12 hour post-dose timepoint at Visit 4 (Week 2). The timepoint not drawn at Visit 4 (Week 2) will be drawn at Visit 12 (Week 10) (3 samples will be drawn at each visit, 2 mL each). For all age groups, blood samples for sparse PK assessments (2 mL each) will be collected while the subject is at the clinic during Visit 3 (Week 1) and at each visit during Visit 5 to Visit 11 (Week 3 to Week 9; 8 samples, 2 mL each). The date and time of each PK sample as well as the date and time of the previous dose of study drug will be recorded on the eCRF.

Table 6 Pharmacokinetic Sampling Schedule

Study Day	Sparse/Serial	Sampling Times
Visit 3/Week 1	Sparse	During clinic visit
Visit 4/Week 2	Serial	• Pre-dose
		Between 2 to 4 hours post-dose ^a
		Between 6 to 8 hours post-dose ^a
		Between 10 to 12 hours post-dose ^a
Visit 5/Week 3	Sparse	During clinic visit
Visit 6/Week 4	Sparse	During clinic visit
Visit 7/Week 5	Sparse	During clinic visit
Visit 8/Week 6	Sparse	During clinic visit
Visit 9/Week 7	Sparse	During clinic visit
Visit 10/Week 8	Sparse	During clinic visit
Visit 11/Week 9	Sparse	During clinic visit
Visit 12/Week 10	Serial	• Pre-dose
		Between 2 to 4 hours post-dose ^a
		Between 6 to 8 hours post-dose ^a
		Between 10 to 12 hours post-dose ^a

a: During Day 1/Visit 2, subjects in Cohort 3 (aged 1 to <6 years) will be randomized in a 1:1 ratio, stratified by treatment group, to either the 6 to 8-hour post-dose PK timepoint or the 10 to 12-hour post-dose PK timepoint during Visit 4/Week 2 and Visit 12/Week 10, to minimize the number of blood draws required during these visits. The timepoint not drawn during Visit 4/Week 2 will be drawn during Visit 12/Week 10.

10 SAFETY ASSESSMENTS

Safety assessments will include monitoring and recording of all AEs and SAEs, laboratory tests, vital signs, and physical examinations during the Core Phase and Extension Phase of the study.

10.1 Adverse Events

An AE is defined as any untoward medical occurrence in a subject administered a pharmaceutical product, which does not necessarily have a causal relationship with this treatment. An AE can therefore be any unfavorable and/or unintended sign (including an abnormal laboratory finding), symptom, or disease temporally associated with the use of an investigational medicinal product, whether or not related to the investigational medicinal product. All AEs, including observed or volunteered problems, complaints, or symptoms, are to be recorded on the appropriate eCRF.

AEs, which include clinical laboratory test variables, will be monitored and documented from the time of informed consent/assent until study participation is complete. Subjects should be instructed to report any AE that they experience to the Investigator. Beginning with the informed consent/assent signature, Investigators should make an assessment for AEs at each visit and record the event on the appropriate AE eCRF. Events associated with disease progression should not be reported as AEs/SAEs. However, if in the Investigator's opinion the disease progression is manifesting in an unusual or uncharacteristic manner, the associated events should be reported as AEs/SAEs, as appropriate.

Wherever possible, a specific disease or syndrome (i.e., diagnosis) rather than individual associated signs and symptoms should be identified by the Investigator and recorded on the eCRF. However, if an observed or reported sign or symptom is not considered a component of a specific disease or syndrome by the Investigator, it should be recorded as a separate AE on the eCRF. Additionally, the condition that led to a medical or surgical procedure (e.g., surgery, endoscopy, tooth extraction, or transfusion) should be recorded as an AE, not the procedure.

Any medical condition already present at Screening should not be reported as an AE unless the medical condition or signs or symptoms present at Screening change in severity, frequency or seriousness at any time during the study. In this case, it should be reported as an AE.

Clinically significant abnormal laboratory or other examination findings that are detected during the study or are present at Screening and significantly worsen during the study should be reported as AEs. The Investigator will exercise his or her medical and scientific judgment in deciding whether an abnormal laboratory finding, or other abnormal assessment is clinically significant. Clinically significant abnormal laboratory values occurring during the clinical study will be followed until repeat tests return to normal, stabilize, or are no longer clinically significant. Any abnormal test that is determined to be an error does not require reporting as an AE.

Clinically significant abnormal findings in PEs subsequent to study drug administration will be reported as AEs.

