1.2 Immune Thrombocytopenia in Adults and Pediatrics

ITP is an autoimmune disorder characterized by low platelet counts caused from a combination of both impaired platelet production and increased peripheral platelet destruction. It has an incidence of as many as 5 out of every 100,000 people (adults or children) and may be either a primary condition or secondary to other causes, such as bacterial or viral infections. The 2019 International Consensus Report on the Investigation and Management of ITP (Provan, 2019) and the American Society of Hematology Guidelines for ITP (Neunert, 2019) define ITP in 3 distinct subsets in accordance to disease duration, which includes:

- Newly Diagnosed ITP: within 3 months of the diagnosis
- Persistent ITP: within 3 to 12 months of the diagnosis
- Chronic ITP: more than 1 year after the diagnosis

The rates of spontaneous remission in adults are much lower than those seen in pediatrics. ITP resolves on its own in 74% of children <1 year of age, 67% of children between 1-6 years of age, and 62% of those between 10-20 years of age, however, it may become chronic and symptomatic in a proportion of children affected (Neunert, 2019). Bleeding events can range from minor events such as bruising and petechiae to more severe events such as hematuria or intracranial hemorrhage which occurs in up to 0.4% of children with ITP; severe bleeding is reported in up to 20% of children. In general, clinical management of ITP depends primarily on its severity, with initial therapy being indicated when platelet counts fall below 30 to 50×10^9 /L with concurrent bleeding symptoms or impact on health-related quality of life (Neunert, 2019; Provan, 2019).

The clinical goal of treatment for ITP is not to normalize platelet counts, but to increase platelet counts to a level that enables patients to live relatively normal and active lives with a manageable risk of bleeding. Current guidelines recommend observation (or watchful waiting) in children with newly diagnosed ITP who have no or only minor bleeding, rather than treatment with corticosteroids or intravenous immune globulin (IVIg). For the treatment of newly diagnosed ITP in children who have non-life-threatening bleeding, agents that decrease platelet destruction (e.g., corticosteroids or immunoglobulins) are recommended as first line treatment. However, these drugs have variable and transient efficacy and significant toxicities.

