3.3 Additional Secondary Efficacy Endpoints

- The percentage of weeks subjects have a platelet count $\geq 50 \times 10^9 / L$ during 12 weeks of treatment in the Core Phase, in the absence of rescue therapy.
- Platelet response at Day 8 (defined by the proportion of subjects with a platelet count $\geq 50 \times 10^9 / L$ at Day 8, in the absence of rescue therapy).

- The percentage of weeks subjects have a platelet count between $\geq 50 \times 10^9 / L$ and $\leq 150 \times 10^9 / L$, during 12 weeks of treatment in the Core Phase, in the absence of rescue therapy.
- The proportion of subjects who require rescue medications during 12 weeks of treatment in the Core Phase of the study.
- Incidence and severity of bleeding symptoms associated with ITP measured using the WHO Bleeding Scale.

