10.2 Adverse Events of Special Interest

The purpose for specifying AESI is to enable further characterization of the clinical course and management of specific events. The Investigator will monitor each subject for clinical and laboratory evidence of pre-defined AESIs throughout their participation in the study, and will report all AESIs listed below within the same timeframe as an SAE (Section 10.4). An AESI may or may not be the consequence of treatment with avatrombopag.

The AESI defined in this protocol include:

- Thromboembolic events (any thrombotic or embolic event, whether arterial or venous).
- Bleeding events (any clinically significant blood loss [e.g., WHO Grade 2 or higher]).

These events will be recorded on the AE eCRF page. The Investigator will assess and record any additional information on the AESI in detail on a SAE form (whether or not the event meets seriousness criteria in Section 10.3), to be submitted within 24 hours of awareness of the event. During the course of the study, additional AESI may be identified and communicated by the Sponsor.

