10.4 Serious Adverse Event Reporting – Procedures for Investigators

10.4.1 Initial Reports

All SAEs, regardless of causal assessment, occurring from the time of informed consent/assent until discharge from the study must be reported to the Sponsor as directed on the SAE reporting form within 24 hours of the knowledge of the occurrence (this refers to any AE that meets any of the aforementioned serious criteria). All SAEs that the Investigator considers causally related to study drug occurring after discharge from the study must be reported to the Sponsor.

To report the SAE, complete the appropriate form for the study and submit to the Sponsor as instructed on the form. It is very important that the form be filled out as completely as possible at the time of the initial report. This includes the Investigator's assessment of causality. The Investigator must notify his/her IRB/IEC of the occurrence of the SAE, in writing, if required by their institution. A copy of this communication must be forwarded to the Sponsor to be filed in the Sponsor's Trial Master File.

The detailed contact information for reporting of SAEs is provided in the Investigator Study File.

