5. PLANNED ANALYSIS

5.1 Changes from Planned Analyses in the Protocol

An exploratory efficacy endpoint was included which was not detailed in the protocol: Month 3 durable platelet response defined as the proportion of subjects achieving at least 3 out of 4 weekly platelet counts $\geq 50 \times 10^9$ /L during the last 4 weeks of the 12 week Treatment Period in the Core Phase in the absence of rescue medication.

Bleeding Adverse Events of Special Interest identified using a MedDRA SMQ were further defined as clinically significant blood loss using reported CTCAE grades instead of WHO bleeding grades, as WHO bleeding grades collected at study visits are not linked to individual adverse events.

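### Protocol 10.1 exempts undefined disease-progression events from AE/SAE reporting; this conflicts with the protocol's own AESI, SAE and other AE rules, and nothing says which prevails

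*Protocol*

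**What the plan says.** Protocol 10.1 states: "Events associated with disease progression should not be reported as AEs/SAEs". The only way back into reporting is "if in the Investigator's opinion the disease progression is manifesting in an unusual or uncharacteristic manner". Disease progression is not defined. Protocol 1.2 says that "ITP is an autoimmune disorder characterized by low platelet counts", and Protocol 3.3 lists as a secondary endpoint "Incidence and severity of bleeding symptoms associated with ITP measured using the WHO Bleeding Scale". On the protocol's own description, a falling count and an ordinary ITP bleed both fit the exemption.

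Other rules point the other way:

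- **Protocol 10.2** names as an AESI "Bleeding events (any clinically significant blood loss [e.g., WHO Grade 2 or higher". It adds that "These events will be recorded on the AE eCRF page" and asks for an SAE form within 24 hours, whether or not the event is serious. It makes no exception by cause.
- **Protocol 10.4.1**: "All SAEs, regardless of causal assessment, occurring from the time of informed consent/assent until discharge from the study must be reported to the Sponsor". Section 10.3 counts a hospital admission as serious.
- **Protocol 10.1**, in its other paragraphs, makes three things AEs: the condition behind a procedure such as a transfusion; a condition present at Screening whose severity, frequency or seriousness changes; and a clinically significant laboratory finding that is new or significantly worse.

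SAP 7.5.2 builds the TEAE, serious-TEAE and AESI tables from AE records. Bleeding AESIs come from the haemorrhage SMQ at CTCAE Grade 3 or higher. SAP 5.1 explains that "WHO bleeding grades collected at study visits are not linked to individual adverse events".

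**The concern.** An exemption for disease progression is workable where progression is defined and captured elsewhere as an outcome. Here it is undefined, and in ITP the natural candidates are the events that other sections want reported. A site that follows 10.1 literally would leave a typical ITP bleed, or an admission for a very low count, off the AE page. A site that follows 10.2 and 10.4.1 would enter it. Both could claim to be compliant.

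At stake are the completeness and site-to-site consistency of the AE, serious-AE and bleeding-AESI tables in a paediatric placebo-controlled trial, and the expedited reporting that starts from an AE or SAE entry. A bleed seen only on the visit WHO scale has no CTCAE grade, seriousness or causality assessment, and the SAP says the visit grade cannot be tied to an individual AE.

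**Working it through.** The plan gives no figure for this point, so the check compares the rules event by event. Each row assumes a course the investigator regards as typical for ITP, so the exception for unusual progression does not apply.

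| Event | 10.1 exemption | Other rules |
|---|---|---|
| Bleed of WHO Grade 2 or higher, no admission | not reported | reported: AESI under 10.2 |
| Same bleed, with admission | not reported | reported: 10.2, and 10.3 with 10.4.1 |
| Admission for low platelets, no bleed | not reported | not an AESI; SAE under 10.3 with 10.4.1; may also meet the worsening rules of 10.1 |
| Transfusion for a falling count, no bleed, no admission | not reported | underlying condition is an AE under 10.1 |
| Minor bleed below the AESI threshold | not reported | AE under 10.1 only if an existing condition has changed |

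**Does the text rank the rules?** No. Section 10.2 does not say that it overrides 10.1, and 10.1 does not except AESIs. The AE definition that opens 10.1 has no carve-out for the disease under study, so a progression event is an AE by definition and is then excluded from reporting.

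**Where is the gap clearest?** In the third row. A site may reasonably treat 10.2 as the specific rule that governs the first two rows. It offers no help for an admission without a bleed.

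**Which outputs depend on AE records?** Under SAP 7.5.2, the TEAE, serious-TEAE and AESI tables. Under Protocol 11.2.3 these are descriptive.

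**Which do not?** The WHO Bleeding Scale is assessed from Visit 2 onward (Protocol 9.4) and tested by CMH (SAP 7.4, Table 3). Local platelet counts are taken at all visits (Protocol 9.5.1). Rescue medication is recorded on the eCRF (Protocol 8.6) and summarised (SAP 7.3.5), and transfusions are summarised with reasons (SAP 7.4).

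**Size.** Let pA and pP be the true proportions with a reportable event, and rA and rP the shares reported. The difference seen is rP·pP − rA·pA. The documents give none of these four values. With assumed values pA = 20% of 54 and pP = 40% of 18:

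- rA = rP = 1: 10.8 and 7.2 subjects, difference 20 points.
- rA = rP = 0.5: 5.4 and 3.6 subjects, difference 10 points.
- rA = rP = 0.25: 2.7 and 1.8 subjects, difference 5 points.
- rA = 1, rP = 0.5: 20% and 20%, difference 0.
- rA = 0.5, rP = 1: 10% and 40%, difference 30 points.

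Equal omission shrinks a true difference in proportion to the share reported. Unequal omission can shrink or enlarge it.

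**The case against.** The strongest reply is that little is lost. Section 10.2 is specific and mandatory, and a specific rule normally governs a general one. The SAP's AESI table counts only CTCAE Grade 3 or higher bleeds, which 10.2 already requires. The planned between-arm bleeding test uses the WHO scale, which 10.1 does not touch. The phrase about causality in 10.4.1 concerns relatedness and does not decide what counts as an AE. Much of this stands and limits the consequence. It does not settle the conflict, because precedence is left for each site to infer and the reading does not reach an admission without a bleed.

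A reader might infer more than the documents support:

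- *That the bleeding comparison is biased or the bleeding data are lost.* The tested endpoint comes from the WHO scale, and rescue and transfusions are recorded separately. The missing link to AEs means only that a visit grade cannot grade an individual AE.
- *That omission falls more on placebo.* No figure shows this. In the adult pool (Protocol Table 1), each bleeding-type term was at least as frequent on active drug: contusion 26% v 18%, epistaxis 19% v 18%, gingival bleeding 13% v 0%, petechiae 11% v 9%. The placebo group there had only 22 subjects.
- *That AE rates will not be comparable with the adult data.* That table comes from labelling. The adult reporting rules are not given, and the SAP plans no such comparison.
- *That IDMC review will be weakened.* The anticipated triggers in Protocol 5.2 are thromboembolic events and serious unexpected adverse reactions, and a typical ITP bleed is not an obvious example of either.

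**Conclusion.** The contradiction is real and should be reconciled. As written, 10.1 excludes from AE and SAE reporting typical ITP events that 10.2, 10.4.1 and other parts of 10.1 require, and nothing ranks these rules. The consequence is possible incompleteness and inconsistency between sites in the descriptive TEAE, serious-TEAE and bleeding-AESI tables and in expedited reporting. The bleeding-AESI table is the least exposed, because it is affected only if a site lets 10.1 override 10.2. The primary endpoint and the WHO-scale bleeding endpoint are unaffected.

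This rests on one inference: that ordinary bleeding and falling counts are what a site would take disease progression to mean in ITP. The protocol's description of the disease supports that reading, but no definition confirms it.

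**What to change.** State in Protocol 10.1 that the progression exemption does not apply to any event that meets the SAE criteria of 10.3 or the AESI criteria of 10.2, or to any event that 10.1 elsewhere already requires as an AE (a condition leading to a transfusion, worsening of an existing condition, clinically significant laboratory worsening). Recording every minor bleed as an AE is not needed to reconcile the passages, and it would largely duplicate the WHO scale.

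For data already collected, check visits with WHO Grade 2 or higher and the rescue and transfusion records against AE entries before database lock, and query mismatches. Because cohorts enrol in sequence, this also helps put earlier subjects on the same basis as later ones. It will not find an admission that involved neither a bleed nor rescue treatment, so sites should be asked about those directly.

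The cost is a minor amendment, with the review that Protocol 13.3 requires, or an eCRF guideline update, plus some additional AE/SAE entries and queries. Endpoints, visits and sample size do not change.

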10.1.1 Method of Detecting Adverse Events and Serious Adverse Events

AEs will be reported by the subject (or, when appropriate, by a healthcare provider, caregiver, surrogate, or the subject's LAR). Care will be taken not to introduce bias when detecting AEs and/or SAEs. Open-ended and non-leading verbal questioning of the subject is the preferred method to inquire about AE occurrences.

